# **PROTOCOL SYNOPSIS**

Title	Robotic versus Electromagnetic Bronchoscopy for Pulmonary
	LesIon AssessmeNT)
Short title	RELIANT
Primary study objective	To compare the diagnostic yield of the Ion TM Endoluminal System (shape sensing catheter bronchoscopy, SSCB) to that of the ILLUMISITE TM Platform (electromagnetic navigational bronchoscopy, EMN) in patients undergoing bronchoscopy with planned biopsy of a peripheral pulmonary lesion.
Study devices	Ion TM Endoluminal System (SSCB); ILLUMISITE TM Platform (EMN).
Design	Single center, open label, pragmatic, non-inferiority, cluster randomized controlled trial.
Study centers	Vanderbilt University Medical Center
Number of clusters	N=202, to be increased if necessary
Inclusion criteria	
 
≥ 18 years of age at time of bronchoscopy.
 
Scheduled for navigational bronchoscopy for the evaluation of a peripheral pulmonary lesion.
 

Exclusion criteria	
 
Enrolled in a different study requiring use of one specific platform
 
Subject declines to participate.
 

Primary endpoint	
 
The primary endpoint will be diagnostic yield obtained from Ion™ or ILLUMISITE™ procedures, defined as the proportion of procedures that result in acquisition of lesional tissue. Lesional tissue: histopathological findings present that readily explain the presence of a pulmonary lesion.
 

Secondary endpoints	1. Duration of the procedure
Exploratory endpoints	
 
Need for additional diagnostic procedures
 
Radiation exposure
 
Diagnostic accuracy at 12-months post-biopsy
 

Safety outcome	
 
Rate of complications (including pneumothorax, bronchopulmonary hemorrhage, respiratory failure, anesthetic complications)
 

Subject follow-up	Patients without malignancy present on biopsy will be followed for up to 12 months as clinically required per standard of care.
Statistical methodology	We assume the diagnostic yield for EMN is 80%. The non-inferiority margin is set at 10%, cluster size of 2, and no intracluster correlation, we need 202 clusters (targeting 425 subjects to reach 202 per arm) to have an 80% power to conclude noninferiority at one-sided type I error rate set at 5%.
Interim analysis	There will be no interim analysis

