Patients not diagnosed with malignancy following bronchoscopic biopsy will be followed clinically per standard of care. We will review their interval chest CT scans to assess the target lesion for progression, regression, or stability for up to 12 months. If any additional biopsies of the target lesion are obtained by alternative means (transthoracic needle biopsy, surgical biopsy), definitive pathological results as previously defined will be compared to the bronchoscopy biopsies.

Study Procedures	Day 1	Within 7 Days	3 Month	6 Months	12 Months
Inclusion/exclusion criteria	X				
Randomization	Х				
Clinical and demographic data	Х				
Adverse events	Х	Х			
Pathology review		Х			
Chest CT	Per SOC		Per SOC	Per SOC	Per SOC
Bronchoscopy	Per SOC				
Follow-up			Per SOC	Per SOC	Per SOC

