In the context of these issues, we believe the only feasible study design for this trial is cluster randomization as previously described. The only additional risks of participation in this study beyond SOC are confidentiality and non-adherence to research consent. All data will be maintained in a secured REDCap database by proceduralists who have already been exposed to the patient's PHI while providing clinical care. The clinical team has a REDCap database in which it is collecting data on these procedures for QI projects and QI analysis. This study will extract these data from the QI systems; no new data are being collected. Research informed consent will be obtained when clinical informed consent is obtained for the procedure. Research informed consent will be scanned, by a study coordinator, into the secured REDCap database and the research paper consent will be kept in a research binder in a locked file cabinet in a locked office. Only the study team will have access to the locked file cabinet. In addition, a note will be written in the patient's electronic medical record stating that the patient was enrolled in this study.

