Biopsies obtained without the use of EMN or SSCB (e.g., sampling of central lymph nodes using the linear endobronchial ultrasound bronchoscope) will not be included in the diagnostic yield calculations. In case of repeat bronchoscopies, only the index bronchoscopy will be included in the diagnostic yield calculation.

Secondary Outcomes

There is one secondary outcome for the trial, which will be collected during the bronchoscopy procedure.

a) Duration of procedure (in minutes), defined as time from the start of airway registration to

the removal of the bronchoscope after completion of navigation procedures.

Exploratory Endpoint(s)

There are three exploratory endpoints that are prespecified. These can be collected during and immediately after the bronchoscopy procedure, and/or during the follow-up period.

a) Need for additional diagnostic procedures. Any diagnostic procedure performed within 12 months of the study bronchoscopy that targets the same peripheral lesion (including repeat bronchoscopy, transthoracic needle biopsy, or surgical lung biopsy) will be considered an additional diagnostic procedure.

1. Repeat biopsies of lesions determined to be malignant by study bronchoscopy which are 1) performed specifically to obtain additional tissue for further testing but that does not change the malignant diagnosis, or 2) therapeutic surgical resection of such lesions, will not be considered additional diagnostic procedures.

b) Radiation exposure, defined as radiation dose delivered to the patient during the study bronchoscopy, recorded as a dose area product (mGy/cm2).

Diagnostic accuracy

Diagnostic accuracy will be assessed for the two devices. Lesions will be categorized as positive (malignant) lesions or negative (specific benign diagnosis). The criterion standard for a negative diagnosis will be no evidence of malignancy at 12-month follow-up (no interval biopsy diagnostic of malignancy, regression on CT or stable size with no plan for repeat diagnostic procedure).

Safety outcome

The main safety outcome for this trial is occurrence of procedure complication(s), defined as the occurrence of any of the following: respiratory failure, pneumothorax, anesthetic complications, and bronchopulmonary hemorrhage.

Safety outcomes will be reported overall and by type.

Statistical analysis plan for **R**obotic versus Electromagnetic Bronchoscopy for Pulmonary LesIon Assessme**NT**: the RELIANT trial PI: [name]

Analysis dataset

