The analysis for the trial will use a intent-to-treat approach. Participants will be evaluated by treatment group as assigned regardless of what was delivered; participants will be excluded if their procedure did not begin, defined as the start of the navigation procedure itself. All eligible participants will be included.

The safety analysis dataset will group participants by device used, regardless of assignment.

Statistical Approach

Our initial analysis will be descriptive in nature, summarizing information that characterizes the cohort and the outcomes. Then, we will proceed with inferential analysis. No interim analyses are planned.

Descriptive Analysis

To characterize the study sample, baseline demographic and clinical data will be described overall and by group. Categorical variables will be described using frequencies and proportions, and continuous variables will be described using means and standard deviations or medians and interquartile ranges, as appropriate. Missingness will be reported for each variable. At a minimum, the following variables will be described at time of enrollment:

- Age (years)
- Gender (male, female, unknown)
- Race (African American, Asian/Pacific Islander, Caucasian, Multiple, Native American, Other, Unknown)
- Ethnicity (Hispanic, Non-Hispanic, Unknown)
- History of cancer (yes/no)
- Smoking History (current, former, never)
- Body mass index (BMI)
- Lesion characteristics
 - o Size (mm)
 - Location (middle vs peripheral)
 - Upper lobe (yes/no)
 - Density (solid, part solid, ground glass opacity)
 - Distance from pleura (cm)
 - Bronchus sign present (yes/no)
- Procedure details

Statistical analysis plan for **R**obotic versus Electromagnetic Bronchoscopy for Pulmonary LesIon AssessmeNT: the RELIANT trial PI: [name]

PI: [name]

- Rapid onsite evaluation (yes/no)
- o Operator
- Digital tomosynthesis (yes/no)
- Cone beam computed tomography (yes/no)
- Biopsy tools

We will describe the outcome variables overall and grouped by study arm using the same approach as for the demographic data. Summary statistics and graphical representations may be displayed, and missingness will be reported for each variable. No statistical comparisons between groups will be done for this descriptive analysis.

Primary analysis

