All model results will be summarized with point estimates and 95% confidence intervals (CIs), which will be emphasized over p-values when reporting the results for secondary outcomes. No adjustments for multiplicity will be made.

Differential effects

To determine whether differences in outcomes are dependent on baseline characteristics, we will introduce interaction terms into the models developed for the main analysis. Specifically, we will test the interaction between device assignment and the subgrouping variable. Each variable will be tested one by one, such that all main effects but only one interaction term is included at a time. The following putative subgrouping variables are prespecified:

- Nodule size (continuous, treatment effects will be estimated at 1.5cm and 3cm)
- Presence of bronchus sign
- Solid vs subsolid nodule
- Peripheral vs central location Peripheral defined as outer 1/3 of chest

Missingness on the primary or secondary outcome is not expected due to the proximity of its measurement with the procedure and its integration into clinical documentation. Procedures missing the primary outcomes will be considered not diagnostic. Missing covariates will be imputed using multiple imputation with predictive mean matching. There may be missingness on exploratory outcomes. For missing exploratory outcomes, a complete case analysis will be performed.

Statistical analysis plan for Robotic versus Electromagnetic Bronchoscopy for Pulmonary LesIon AssessmeNT: the RELIANT trial

PI: [name]

Diagnostic accuracy

Diagnostic test statistics (e.g., sensitivity, specificity, predictive values, likelihood ratios) will be reported for the two devices. In addition, accuracy of the diagnosis may be modeled using a generalized linear model to explore whether participant or lesion features are predictive of procedure success, as described for the differential effects analysis.

Summary

The results of this study will help to determine whether there is a difference between these two diagnostic bronchoscopy platforms for patient outcomes. The analysis approach we describe is selected based on the trial's pragmatic nature and specifically the intent to understand if the diagnostic yield of the IonTM Endoluminal System (SSCB) is not inferior to the ILLUMISITETM Platform (EMN) in patients undergoing bronchoscopy to biopsy a peripheral lung lesion.

Version and Revision Log

7/12/2022	Version 1: developed with and approved by [name].

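### Complete case analysis of the two 12-month exploratory endpoints drops mainly non-malignant index results and conflicts with the protocol's accuracy denominator

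*SAP*

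**What the plan says.** **Who is followed.** The Protocol Synopsis says: "Patients without malignancy present on biopsy will be followed for up to 12 months as clinically required per standard of care". Study Procedures repeats this ("Patients not diagnosed with malignancy following bronchoscopic biopsy will be followed clinically per standard of care") and names the data source: "We will review their interval chest CT scans to assess the target lesion for progression, regression, or stability for up to 12 months". The study calendar marks CT and follow-up at 3, 6 and 12 months as standard of care.

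**Accuracy.** Protocol, Outcomes Definitions, puts malignant biopsies in the numerator as true positives. It adds specific benign results only if there is no evidence of malignancy at 12 months. The denominator is all biopsied lesions. The SAP sorts lesions into malignant and specific benign and uses the same 12-month standard for a negative. It does not say where non-diagnostic biopsies go.

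**Need for additional procedures.** The SAP counts "Any diagnostic procedure performed within 12 months of the study bronchoscopy that targets the same peripheral lesion". For a lesion already shown malignant, both documents exempt therapeutic resection, and also resampling for further testing that leaves the diagnosis unchanged.

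**Missing data.** At the end of its Differential effects section the SAP says "There may be missingness on exploratory outcomes", then "For missing exploratory outcomes, a complete case analysis will be performed". Its Descriptive Analysis section adds: "Summary statistics and graphical representations may be displayed, and missingness will be reported for each variable". No imputation, weighting, bounds or sensitivity analysis is planned for these two endpoints.

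**The concern.** Whether a patient's 12-month status can be missing depends on the index result. A malignant result settles accuracy at once and makes need almost always a no. A specific benign or non-diagnostic result leaves one or both endpoints open for up to a year, with no study visit to close them. Deleting the unknowns therefore removes non-malignant patients and keeps nearly all malignant ones. That biases each device's estimate even if loss is random among non-malignant patients.

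The planned covariates (lesion size, density, peripheral location, bronchus sign, operator) do not include the index result, so model adjustment does not undo the selection. The smaller denominator also contradicts the protocol's definition of accuracy.

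At stake are the accuracy and further-procedure figures published for each platform. The protocol's Objectives section lists absence of malignancy at 12 months and need for additional procedures among the comparisons, although both documents class the endpoints as exploratory.

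**Working it through.** **Plan's own figure.** There is none for the 12-month endpoints or their loss. The protocol's sample-size table does reproduce: a Farrington-Manning score test with 202 per arm, 80% v 80%, margin 10 points and one-sided 5% gives power 0.80327. It concerns diagnostic yield and is not affected here.

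**Assumed inputs (none is in the documents, except that a 20% non-diagnostic share matches the planned 80% yield).**
- Arm A: malignant M = 0.60, specific benign B = 0.20, non-diagnostic ND = 0.20.
- Arm B: M = 0.50, B = 0.20, ND = 0.30.
- Further procedure in 10% of benign and 50% of non-diagnostic results, none counted after a malignant one. 95% of benign results are confirmed.
- Loss L = 0.30, among non-malignant results only and random within them.
- Every included procedure yields a biopsy, so one denominator serves both endpoints.

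**Need.** True = 0.10B + 0.50ND. Complete case = (1−L) × true / [M + (1−L)(B+ND)].
- A: true 0.02 + 0.10 = 12.0%; complete case 0.084/0.88 = 9.5%.
- B: true 0.02 + 0.15 = 17.0%; complete case 0.119/0.85 = 14.0%.
- A with 10% loss: 0.108/0.96 = 11.3%; with 40% loss: 0.072/0.84 = 8.6%.

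**Accuracy.** True = M + 0.95B: A 79.0%, B 69.0%. The complete case value depends on a choice that the SAP leaves open.
- Lost non-diagnostic results dropped too, (M + 0.95B(1−L)) / [M + (1−L)(B+ND)]: A 0.733/0.88 = 83.3%; B 0.633/0.85 = 74.5%.
- Only lost benign results dropped, (M + 0.95B(1−L)) / [M + (1−L)B + ND]: A 0.733/0.94 = 78.0%; B 0.633/0.94 = 67.3%.

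**Sensitivity (promised in the SAP).** Suppose 40% of non-diagnostic lesions are malignant and count as missed, and lost ones are dropped. Arm A's missed share is 0.05 × 0.20 + 0.40 × 0.20 = 0.09. Sensitivity moves from 0.60/0.69 = 87.0% to 0.60/(0.60 + 0.7 × 0.09) = 90.5%.

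**Direction if loss depends on outcome.** In arm A, let 5% of those with a further procedure be lost and 30% of the other non-malignant patients. Need reads 0.114/(0.60 + 0.114 + 0.196) = 12.5%, above the true 12.0%. In arm B it reads 0.1615/(0.50 + 0.1615 + 0.231) = 18.1% against 17.0%.

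**Device contrast.**
- Arms A and B at 30% loss: the gap in need goes from 5.0 to 4.5 points. The gap in accuracy goes from 10.0 to 8.8 or 10.6.
- Two identical arms (A's inputs) with equal loss: no spurious difference.
- Two identical arms with 10% v 30% loss: need 11.3% v 9.5%, a spurious −1.7 points before rounding. Accuracy 80.3% v 83.3% (+3.0) or 78.7% v 78.0% (−0.7).

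**Cross-check with other assumptions.** M 55%, B 25%, ND 20%, 95% of benign results confirmed, further procedure in 60% of ND and 10% of B, 30% loss. Need falls from 14.5% to 11.7%; accuracy moves from 78.8% to 82.8% or 77.4%.

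**The case against.** The strongest reply is that the trial compares devices, and the comparison barely moves. In the A v B example the unadjusted odds ratio for need is 0.67 with full data and 0.65 with complete cases. For accuracy it is 1.69 against 1.71 or 1.72. With 202 per arm, the 95% half-widths on the two true differences are about 6.8 and 8.5 points, far larger than the shifts. The plan assumes 80% yield in both arms, no loss rate is documented, missingness will be reported, and the endpoints are exploratory. All of this stands. It limits the size and weight of the point. It does not remove the bias in each device's own figures or the conflict over the denominator, and reporting missingness discloses the problem without correcting it.

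Several stronger readings are tempting but unsupported:
- *Only non-malignant patients are followed.* The documents describe follow-up for that group but do not say that others go unfollowed, and the calendar row is unrestricted.
- *A malignant biopsy fully settles both endpoints.* For need, the exemption covers only resampling that leaves the diagnosis unchanged and therapeutic resection.
- *Loss will be heavy.* The statement "no new data are being collected" belongs to the consent and confidentiality rationale, and Study Procedures does plan a review of CTs and later biopsies. Meeting patients on the procedure day explains the timing of enrolment, not loss.
- *Need is always understated.* The 12.5% result above shows that it can be overstated.

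**Conclusion.** The point holds as a limited one. For the two 12-month exploratory endpoints, missing status will fall mainly on non-malignant index results. Complete case analysis then estimates each device's accuracy and need in a malignancy-enriched set, and it departs from the protocol's denominator of all biopsied lesions.

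The size is illustrative because every loss figure is assumed. At 30% loss in arm A, need of 12.0% reads 9.5%, and accuracy of 79.0% reads 83.3% or 78.0%. The direction depends on who is lost and on how non-diagnostic biopsies are counted.

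A reader might infer that the device comparison is necessarily distorted, or that the non-inferiority conclusion is at risk. Neither follows. The contrast is biased only if loss or the non-malignant share differs by arm. The primary endpoint (yield) and the secondary endpoint (procedure duration) do not use 12-month status.

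**What to change.** 1. **Reconcile the documents.** Keep all biopsied lesions as the accuracy denominator, as in the protocol's Outcomes Definitions, and all included procedures for need. State how non-diagnostic biopsies enter accuracy.
2. **Replace complete case analysis for these two endpoints** with estimation conditional on index result (malignant, specific benign, non-diagnostic) within arm. Stratified reweighting, inverse-probability weights, or multiple imputation that includes the index result would each serve, and can feed the planned mixed model. The index result belongs in the weighting or imputation step. As a covariate in the outcome model it would adjust away part of the device effect. In arm A with random loss, reweighting returns 0.60 × 0 + 0.20 × 0.10 + 0.20 × 0.50 = 12.0%.
3. **Report 12-month ascertainment** by arm and index-result category, and define when status counts as known.
4. **Add best-case and worst-case bounds.** Reweighting corrects only the loss that the index result explains. In the outcome-dependent example (5% v 30% loss) the reweighted need in arm A is 0.20 × 0.019/0.145 + 0.20 × 0.095/0.165 = 14.1%, further from 12.0% than the complete case 12.5%. So the bounds are not optional. For arm A at 30% random loss they are 8.4% to 20.4% for need (0.084, plus up to 0.30 × 0.40 = 0.12). For accuracy they are 73.3% to 79.3% (0.733, plus up to 0.30 × 0.20 = 0.06).

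**Cost.** An SAP amendment and a little more analysis work, using index results already collected, with no extra visits or patients. Intervals will be slightly wider, and the bounds may be wide if loss is high.
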